### Secondary Outcomes

- Uptake of modern family planning methods at 6 months postpartum
- Infant immunized per EPI scheduled at 1 year
- Completion of IPTp2 malaria prophylaxis during pregnancy

**Aim 3:** To evaluate the clinical outcomes of mothers and their newborns (e.g. decrease in maternal morbidities and perinatal and neonatal mortality)

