### Primary Outcomes

- Maternal pregnancy-related morbidities (puerperal sepsis, delayed postpartum hemorrhage)
- Birth outcome (stillbirth, live birth, early neonatal mortality)

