### **3.0 Research Methods and Study Design**

To accomplish our aims we propose a cluster randomized controlled trial (cRCT) in the Eastern District of Ghana. The study is designed in collaboration with the Dodowa Health Research Center under the direction of [name] (Co-PI). Health facilities were selected based the number of deliveries and average gestational age of women in each facility and matched so that each pair of facilities are similar to each other with regard to these matching factors. For each pair of facilities, one will randomly be assigned to group ANC (intervention) and the other to routine, individual ANC (control). The locations of the chosen facilities ensure that participating facilities will be far enough apart to minimize the likelihood of cross-group contamination. The unit of randomization is the health facility stratified by site and gestational age. Cluster randomization will be produced through nbpMatching package from R software. During the study, 1680 participants will be randomized into 120 groups of 12 to 14 women of the same gestational age at the cluster site. This will result in approximately 8-10 groups per site during the study period.

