## Measures

Time Point	Domain	Data collection
T0 – Baseline	Demographic Characteristics (Age, gravida, living children, marital status, age at marriage, pregnancy history, medical history)	Face-to-face Survey
	Self-efficacy	
	Recognize problems and understands health information	Face-to-face Survey
	Care-seeking history	Face-to-face Survey
	Educational Background	
	Level of Education	Face-to-face Survey
	Prior Knowledge	
	Ability to identify danger signs/BPCR	Face-to-face Survey
	Health Literacy Skills (understanding, engagement with health system)	Face-to-face Survey
	Ecological Influences (social support, community and family resources)	Face-to-face Survey
T1 – Third trimester	Comprehension of Stimuli (identification of danger signs, BPCR)	Face-to-face Survey
	Self-determination	
	Intent to use family planning / preparation for birth	Face-to-face Survey
	Two or more tetanus toxoid vaccines / Completion of ITP 2 malaria prophylaxis	ANC Card
T2 – Post birth	Clinical Health Related Outcomes (Place of birth, hemoglobin levels, newborn birth weight, maternal & newborn morbidities, stillbirth, postpartum visit within 2 days post birth)	ANC Card
	Self-determination	
	Attendance at 4 or more ANC visits	ANC Card
	Adherence to care - Number of ANC Visits	ANC Card
	Health Related Behavior (Maternal and newborn postpartum visits)	Survey
	Clinical Health Related Outcomes (Perinatal mortality (<7 days), maternal morbidities)	ANC Card
T3 – Six months postpartum	Health Related Behavior (Uptake of modern family planning, exclusive breastfeeding, 4 postnatal check-ups completed on both mother and newborn in first 6 weeks)	Survey via phone
	Clinical Health Related Outcomes (Neonatal mortality(<28 days), maternal morbidities)	Survey via phone
T4 – One year postpartum	Health Related Behavior (Repeat pregnancy)	Survey via phone
	Clinical Health Related Outcomes (Infant immunized per EPI schedule; maternal morbidities)	Self-report Survey via phone

During all visits midwives will record Clinical Health Related Outcomes (Place of birth, hemoglobin levels, newborn birth weight, maternal & newborn morbidities, stillbirth, postpartum visit within 2 days post birth) on the women's ANC card. These data will be collected by the RA during all study visits except baseline.

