### 4.0 Data Analysis (Aims 1-3)

Data on all patients randomly assigned to the intervention or control groups will be analyzed on an intention-to-treat basis. Deviations from randomized allocation will be reported. Summary statistics based on mean, standard deviation or frequency will be used to characterize the sample distribution of each arm. Proper transformations will be investigated and taken if the sample distributions of continuous variables violate the normality assumption. For Aims 1-3, generalized linear mixed models (GLMMs) will be used to test the differences between the two arms since cluster randomized control design is used. There are four components in GLMMs: outcome variable, fixed effects, random effect, and link function. The fixed effects include explanatory variable and covariates. In this study, all three aims have the same explanatory variable which is a binary variable indicating the arm to which women are assigned. The study sites, gestational age, and women's demographic variables such as education or literacy, marital status, pregnancy history, and medical history will be added to the GLMMs as covariates to increase the precision of estimates. The random effect is the 14 facilities. In this study, a random intercept model will be used to account for the cluster effect. The outcome variables and link functions in GLMMs depends on aims and are described below. The construct of GLMMs is to test if the explanatory variable is significant at 0.05 level using likelihood ratio test.

For **Aim 1** to quantify differences in the recognition of pregnancy and newborn danger signs and knowledge of recommended action steps, the BPCR Index will be measured at enrollment and third trimester. We will add baseline data as covariates. The logit link function will be used for each binary BPCR question to test the efficacy of the group-based ANC method. The identity link function will be used when the outcome variable is a summary statistic of the BPCR Index. When the p-value of the explanatory variable is less than 0.05, we will declare a significant difference between the two arms. Average changes in BPCR summary statistics or odds ratio in each question will be used to quantify the effect of the group-based ANC intervention.

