For **Aim 2** of assessing behavioral differences in care-seeking patterns between the two arms, the outcome variables are number of attendances in ANC visits, facility birth, and postnatal/partum care. For the attendance outcome variable, identity function will be used. For facility birth or postnatal/partum care, the logit link function is used. When the p-value of the explanatory variable is less than 0.05, we will declare a significant difference between the two arms. The effect of group-based ANC on attendances is quantified by the average difference. The effects of group-based ANC on facility birth and postnatal/partum care are quantified by odds ratio. For the secondary outcomes in aim 2, the logit or identity links will be used in the way similar to the primary outcomes.

For **Aim 3** to evaluate the clinical outcomes of mothers and their newborns, the outcome variables are maternal pregnancy-related morbidities and newborn birth status. For maternal morbidities, the logit link function is used. Since the newborn birth status is classified into three categories (stillbirth, live birth, and early neonatal mortality), cumulative logit link function is used. When the explanatory variable is significant at 0.05, the effect of group-based ANC on maternal pregnancy-related morbidities and newborn birth status are interpreted using odds ratio. We will illustrate the difference between outcomes using odds ratios for each pair of newborn birth status. The secondary outcomes are analyzed similarly using identity or logit link functions.

For the multiple outcomes in the same family, we will conduct direct inference using the Holm's multiple testing procedure to control familywise error rate at 0.05 level. The GLMM analysis will be carried out using lme4 package from R software. All findings will be reported using the Consolidated Standards of Reporting Trials (CONSORT) statement as a guide. Full transparency will be provided when reporting experimental details so that others may reproduce and extend our findings. We will register the study with clinicaltrials.gov and disclose all demographic and baseline characteristics, as well as primary and secondary outcomes.

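### The Aim 3 primary birth outcome has a cumulative logit but no stated severity order or exclusive categories; in the only order given, a mortality benefit can cancel or reverse.

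*Combined protocol and SAP*

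**What the plan says.** Section 2.0 lists, as an Aim 3 primary outcome, "Birth outcome (stillbirth, live birth, early neonatal mortality"). Section 4.0 takes the same three categories in the same order and gives their number as the reason for the link: "Since the newborn birth status is classified into three categories (stillbirth, live birth, and early neonatal mortality), cumulative logit link function is used". The general rule in section 4.0 is to "test if the explanatory variable is significant at 0.05 level using likelihood ratio test". For Aim 3, once the arm effect is significant, its effects on maternal morbidities and "newborn birth status are interpreted using odds ratio". The plan adds: "We will illustrate the difference between outcomes using odds ratios for each pair of newborn birth status". No test is attached to those pairwise odds ratios.

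The stated purpose of Aim 3 includes a "decrease in maternal morbidities and perinatal and neonatal mortality". In the Measures table (section 3.3), the T2 row includes stillbirth and "Perinatal mortality (<7 days), maternal morbidities", so a 7-day window for early death is available. Nothing in the document ranks the three categories, says whether the arm effect is common to both cut-points, or says that live birth means live-born and surviving the first week.

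**The concern.** A cumulative logit divides an ordered scale at successive cut-points. In the listed order the cut-points are stillbirth versus the rest, and stillbirth or live birth versus early neonatal death. Survival is in the middle. Preventing stillbirths moves births up the scale and preventing early neonatal deaths moves births down it. A single arm coefficient averages two benefits of opposite sign.

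As worded, a baby who dies in the first week was also born alive and fits two categories. The promised pairwise odds ratios are also not what a common-slope cumulative logit estimates: it gives one odds ratio shared by both cut-points.

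This is the mortality endpoint of Aim 3. If its test can return no effect, or an odds ratio on the wrong side of 1, when both kinds of death fall, the aim cannot be read from it. If the order is chosen after data are seen, the sign of a primary result depends on a choice that was not pre-specified.

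**Working it through.** The plan gives no event rate, effect size or power for this outcome, so there is no figure to reproduce. The check is of the mechanism.

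**Inputs from the document.** Categories, order, link and likelihood ratio test: sections 2.0 and 4.0. Sample size: "1680 participants will be randomized into 120 groups of 12 to 14 women" (section 3.0). Effects seen elsewhere: 9% fewer stillbirths and 23% lower neonatal mortality with community women's groups (section 1.2, background rather than a design assumption).

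**Assumptions.** 1680 / 2 = 840 women per arm. Control risks of stillbirth (SB) and early neonatal death (END) total 4%. The neonatal reduction is applied to END. Clustering and covariates are ignored, which flatters power but does not drive the cancellation.

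**Model.** logit P(Y ≤ j) = α_j + β·arm for j = 1, 2, with common OR = exp(β), fitted by maximum likelihood to expected proportions.

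**Why it cancels (2% + 2%, both halved to 1% + 1%).**
- Cut-point 1, SB versus the rest: (0.01/0.99) / (0.02/0.98) = 0.495.
- Cut-point 2, SB or live birth versus END: (0.99/0.01) / (0.98/0.02) = 99/49 = 2.02.
- 0.495 × 2.02 = 1.00, so the two are reciprocal and the common OR is 1.00.
- Perinatal death versus survival: (0.02/0.98) / (0.04/0.96) = 0.49.

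**Results.** The severity order is SB, END, survivor.

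| Control SB + END | Reduction SB, END | Listed-order common OR | Perinatal death OR | Severity-order OR |
|---|---|---|---|---|
| 2.5% + 1.5% | 50%, 50% | 0.84 | 0.49 | 0.49 |
| 2% + 2% | 50%, 50% | 1.00 | 0.49 | 0.49 |
| 1.5% + 2.5% | 50%, 50% | 1.19 | 0.49 | 0.49 |
| 2.5% + 1.5% | 9%, 23% | 1.03 | 0.85 | 0.85 |
| 2% + 2% | 9%, 23% | 1.08 | 0.83 | 0.84 |
| 1.5% + 2.5% | 9%, 23% | 1.13 | 0.82 | 0.82 |

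Binary check for the fifth row: 0.02 × 0.91 + 0.02 × 0.77 = 0.0336; (0.0336/0.9664) / (0.04/0.96) = 0.83.

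With stillbirth at the bad end of the scale, an OR above 1 would be read as harm. At 2% + 2%, halving stillbirth alone gives 0.75 and halving END alone gives 1.34: two benefits, opposite directions.

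**Test.** At 2% + 2% with both halved, the 1-df likelihood ratio test at 0.05 rejects 5.0% of the time in the listed order, which is its alpha. Power is about 68% in severity order and about 67% for binary perinatal death.

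**The case against.** A reader might infer that the planned analysis will miss or reverse a benefit. The document does not support that. The categories appear in a parenthetical list, and nowhere is that list said to be the ordinal coding. An analyst who used severity order would get 0.49, as good as the binary outcome. Nor does the plan say that the arm effect is common to both cut-points. With separate effects at 2% + 2% halved, the odds ratios are 0.495 for stillbirth versus the rest and 0.495 for early neonatal death versus the rest, and the 2-df test has about 57% power. Both objections stand and make the failure conditional. They do not remove the defect: the only order on paper is the harmful one, a common slope is the usual default, and neither choice is pre-specified.

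The overlap of categories is a wording gap. Classification into three categories suggests one per newborn, and a one-line definition settles it.

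The pairwise odds ratios would show the benefit: at 2% + 2% halved, (0.01/0.98) / (0.02/0.96) = 0.49 for each death against survival. But they are illustrative, untested and not supplied by a common-slope model.

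The magnitudes rest on assumed risks. Exact cancellation needs similar rates and similar relative reductions, and halving both deaths is far larger than the effects in section 1.2. With those effects at 2% + 2%, even a correct analysis has only about 10% power before clustering. In that range the repair would seldom change the test's conclusion, though it would change the direction of the estimate.

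A reader might also infer, from enrolment before 20 weeks, that many pregnancy losses fit no category. The document gives no gestational threshold for stillbirth and no loss rate, so no size can be put on this and the point does not rely on it.

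**Conclusion.** The point holds in conditional form. What is certain from the text is that a primary outcome is given an ordinal model without a severity order, without exclusive category definitions, and without saying whether the arm effect is common to both cut-points. If the listed order is used with a common effect, an odds ratio of 0.49 for perinatal death becomes 0.84 to 1.19 in the cases shown, and 0.82 to 0.85 becomes 1.03 to 1.13. These figures assume 4% total control risk, equal arms and no clustering. This is more than missing detail, because the only order on paper makes the default model fail for the effect that Aim 3 is meant to detect. It should be settled before outcome data are analysed.

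**What to change.** Define three exclusive categories: stillbirth; live-born and died before 7 days; live-born and alive at 7 days. Make the primary test a mixed logistic model of perinatal death (stillbirth or death before 7 days) versus alive at 7 days, with the planned facility random intercept and covariates. Report stillbirth and early neonatal death as separate binary outcomes, and state the denominator of each.

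Two alternatives are equally acceptable:
- Keep the three categories with the order stillbirth, early neonatal death, survivor written into section 4.0, state that the arm effect is common, and drop the promise of pairwise odds ratios.
- Use a multinomial model, which delivers the pairwise odds ratios, and name its joint test of arm as the primary test.

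Cost: section 4.0 and the primary outcome wording in section 2.0 both change, and the binary version merges two kinds of death in the primary test. The Measures table already includes stillbirth and death before 7 days. Because the T2 visit may take place straight after birth, the plan should say how status at day 7 is confirmed when T2 falls earlier; the T3 interview already covers neonatal mortality.

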#### **4.1 Data Analysis (Process Evaluation):**

Steckler et al. will guide our analysis of our process evaluation data. Qualitative data will be obtained from semi-structured interviews. All qualitative data will be collected by trained RAs,

transcribed verbatim into English (leaving key phrases that are difficult to translate intact, with the closest approximate meaning put in parentheses in the transcription). No data will be collected by clinical providers. All transcripts will be stored on a password protected server. All data from semi-structured interviews will be entered into N-Vivo qualitative software to assist with the identification of key themes. Structured observations will be recorded and summarized for key points. The use of an audit trail composed of methodological and analytical documentation and validation with colleagues will be used to achieve validity.

#### **4.2 Risks or Discomforts and Benefits**

There are minimal risks to participants in this study. There is a rare risk of breach of confidentiality, emotional discomfort, and lack of privacy in the study that will be minimized as outlined below. For the survey portion of the study, participants will be informed in the informed consent as well as verbally in advance of the possibility of questions regarding sensitive subject matters that may make them feel uncomfortable. They will be told that they may skip any question that they find too distressing and/or withdraw from the survey at any time. The Ghanaian RAs will be trained to monitor and to provide emotional support. If a participant experiences emotional discomfort while responding to the questions, the RAs will offer support, determine whether it is appropriate to continue and/or provide an appropriate local referral if needed. Local referrals sources will be determined in advance and supplied to the RAs at the time of the study. All forms will be retained by the Ghanaian RA in a locked office, transported to the US in a locked carry-on that is kept with the research team member at all times, and then will be stored in a secure location in a locked file cabinet in the locked office of the primary investigator at the University of Michigan after study completion to protect confidentiality.

#### **4.3 Incentives**

Incentives for participants will include baby layette items (e.g. baby hat, blanket, socks, tote bag) given at each time point.

#### **4.4 Confidentiality of Data, Processes for Anonymizing Data**

To maximize data confidentiality and participant protection in the proposed project, all project staff will be trained in these requirements and the importance of confidentiality emphasized on a regular basis. Participant confidentiality will be protected in that we are not recording names of participants on any paper study material or data collection tools. All study materials will be stored in a locked space every evening and all data will be encrypted. Data will be stored on an encrypted and password protected tablet in a locked space.

Focus groups participants will be consented individually before they enter the focus group room so they may choose whether they want to participate. The group will be conducted in a private setting, and names will not be used during the discussion. Participants will be reminded that the discussion is private and they should avoid discussing the focus with others outside the group. Audio tapes will be transcribed and will be de-identified; tapes will be immediately destroyed after transcription. Prior to transcription, all tapes will be stored in a locked file cabinet in a locked

office in the Dodowa Health Research Center. Access to the cabinet will be restricted to study investigators and the DHRC study team.

#### **4.5 Data Storage and Management**

Data will be considered strictly confidential and will be entered into an electronic record using a secure tablet with password-protected access. Prior to data collection, tablets will be encrypted to ensure all data is securely stored. Once a tablet is encrypted, a one-time process that is initiated from the tablet's settings page, users will be asked to enter a pin every time the device is turned on and data will only be available when the device is unlocked.

Data will be stored on a secure, cloud-based server, accessible only to trained members of the research team. No names will be included in any recorded data, instead using individual tracking numbers that will be kept in a separate encrypted data file for the purposes of long-term follow-up. There will be two contact lists: first, a full contact list that contains the participant's name, phone number, and study ID. This paper list will be kept in a locked file cabinet in a locked office. The second contact list (electronic list), for the purpose of study visits and data collection, will include only the participant's first name and study ID number. The RA will travel to the field for data collection carrying only a password protected file on the encrypted tablet to meet with participants.

Access will be available only to study members working directly with participants for follow-up data collection. We will destroy all links between respondents and survey data after project completion. Study material transported back to UM will be in a locked briefcase that will be carried onto the plane and remain with the research team at all times.

#### **4.6 Long-term data storage and management; Clarity of data ownership**

Upon completion of the project all data - stripped of any potential identifiers - will be kept in University of Michigan's Deep Blue, a permanent, publically available data repository.

#### **5.0 Ethical considerations**

This study will begin after approval from the University of Michigan Health Sciences Behavioral Sciences Institutional Review Board (IRB) and Ghana Health Service. An experienced, interdisciplinary and transnational team of researchers with a long-standing history of collaborations will carry out the proposed study. This innovative interdisciplinary group—nurse midwives, public health experts, and researchers from the United States and Ghana—bring a wealth of knowledge and skills to the proposed study. As required by the University of Michigan (regardless of the country of residence), all research staff, including principal investigators, coinvestigators, and research assistants on research projects that involve human study participants must complete the online Program for Education and Evaluation in Responsible Research and Scholarship (PEERRS) or equivalent, and must have their human subjects certification renewed every three years. The Ethics Boards at Ghana Health Services and DHRC are responsible to oversee the research activity of the DHRC study members.
